#### 4.3 Toxicity Management & Dose Delays/Modifications

Any patient who receives at least one dose of study therapy will be evaluable for toxicity endpoints. Each patient will be assessed for the development of toxicity according to the timeframe referenced in the Schedule of Events table (section 5). Toxicity will be assessed according to CTCAE v5.0.

- In order to start a new cycle of therapy a patient must have platelets  $\geq$  100,000, ANC  $\geq$  1,000, and resolution of all treatment-related toxicity (except alopecia) to Grade 2 or less or to baseline when baseline was more than Grade 2.
- A dose can be delayed for up to 7 days for resolution of toxicity. The subsequent doses will be delayed so as not to shorten the dosing interval.
- If the dose cannot be given within 7 days of scheduled time it should be omitted. Patients who miss 3 consecutive doses will be removed from the study.
- Patients will be withdrawn from the study if they fail to recover to CTCAE 5.0  $\leq$  1 or baseline from a drug-related toxicity (except alopecia)  $\leq$  4 weeks.
- Patients can have a maximum of 2 dose reductions for drug-related toxicity beyond which they will be removed from the study. Dose reduction should follow the dose levels displayed in the table below. Re-escalation is not permitted.

Dose modifications

Dose Level	Dose of sEphB4-HSA
Starting Dose	1000mg IV over 60 min every 2 weeks
-1	750 mg IV over 60 min every 2 weeks
-2	500 mg IV over 60 min every 2 weeks

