## NU Study Number: NU 18U10

vomiting, and diarrhea		drug will require immediate dose interruption. Treatment will be withheld until toxicities have resolved to Grade 1 or baseline. After resolution of the toxicity, a one dose level reduction will be initiated.
AST/ALT	Grade 3	Grade 3 AST and/or ALT that does not represent at least a two grade increase from baseline – hold therapy, recheck weekly. If AST and ALT return to baseline grade within 7 days, retreat at same dose level. If AST and ALT do not return to baseline within 7 days, treatment should be restarted once AST and ALT have returned to baseline and dose should be reduced by one level.  Grade 3 AST and/or ALT that represents at least a two grade increase from baseline or $AST/ALT \geq 10 \times UNL$ –hold therapy, recheck weekly, initiate retreatment when resolved to baseline with one dose level reduction.
	Grade 4	Grade 4 AST and/or ALT– hold therapy, recheck weekly, initiate retreatment when resolved to baseline with a one level dose reduction.  Any grade AST or ALT that represents a doubling from baseline AND that is concurrent with a doubling of the total bilirubin- hold therapy, recheck weekly, initiate retreatment when resolved to baseline grade or grade 1 with one level dose reduction.
	Grade 2	Patients with grade 2 hypertension as evidenced by two or more different measurements that are at least one our apart should be initiated on antihypertensive therapy per the treating physician. BP should be rechecked in one week after initiation of antihypertensive therapy; if SBP is still $>150$ and/or DBP is $> 100$ , physician should increase the dose of the antihypertensive or add a second antihypertensive drug as indicated.
Hypertension 	Grade 3	First occurrence, patients may continue on treatment while their antihypertensive therapy is optimized. A second occurrence of grade 3 hypertension despite antihypertensive therapy would require holding treatment with sEphB4-HSA until hypertension returns to $\leq$ grade 2 at which point treatment can be resumed with one dose reduction.
	Grade 4	Withhold study drug. Optimal management with intensive IV support in ICU.
Platelets	Grade 3/4	Hold therapy, recheck weekly, initiate retreatment when resolved to Grade 1 or less and restart treatment with a one level dose reduction.

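### AST/ALT rows of 4.3.1: the release of the combined enzyme-and-bilirubin hold can already be met when the hold is triggered, and one Grade 3 pattern receives two different restart doses

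*Combined protocol and SAP*

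**What the plan says.** The instructions are in the AST/ALT rows of the dose-modification table in protocol section 4.3.1.

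- **Combined rule.** Trigger: "Any grade AST or ALT that represents a doubling from baseline AND that is concurrent with a doubling of the total bilirubin- hold therapy", followed by a weekly recheck. Release: "initiate retreatment when resolved to baseline grade or grade 1 with one level dose reduction".
- **Grade 3, first sentence.** It covers "Grade 3 AST and/or ALT that does not represent at least a two grade increase from baseline". Therapy is held. "If AST and ALT return to baseline grade within 7 days, retreat at same dose level"; if not, "treatment should be restarted once AST and ALT have returned to baseline and dose should be reduced by one level".
- **Grade 3, second sentence.** It covers "Grade 3 AST and/or ALT that represents at least a two grade increase from baseline or" a value of at least 10 × ULN. Restart is one level lower after return to baseline, with no 7-day exception.
- **Grade 4 enzymes alone.** Hold, recheck weekly, then "initiate retreatment when resolved to baseline with a one level dose reduction".

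Three other sections bear on these rows. Section 4.3 sets dose levels of 1000, 750 and 500 mg, allows at most two reductions before removal, and states "Re-escalation is not permitted". Section 4.3.2 discontinues therapy for Hy's Law (AST or ALT above 3 × ULN with bilirubin above 2 × ULN and no other cause) and for Grade 4 toxicity with listed exceptions. Section 3.1.9 admits patients with AST/ALT up to 3 × ULN, or up to 5 × ULN with liver metastases.

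**The concern.** The combined rule is triggered by a relative change (two doublings from baseline) but released by an absolute grade. A rule built that way can be satisfied by the state that set it off. If it is, the hold has no defined end point of its own, and the part that clearly remains is a dose reduction that cannot be reversed. This rule matters most for early combined rises that are too small for the Hy's Law rule.

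The two Grade 3 sentences raise a different problem. The first has no upper limit, and the second adds the 10 × ULN limb with the word *or*. One laboratory course can therefore fall under both, and the two sentences give different doses. With three centers applying the table, two of them could each follow the text and treat the same course differently. The difference counts against the limit of two reductions.

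**Working it through.** No sample size, power or error rate is involved, so the check applies each sentence literally to every combination of conditions.

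**1. Combined rule.** Inputs: baseline grade 0, 1 or 2; event grade from baseline grade up to 4; both doublings present. That gives 5 + 4 + 3 = 12 combinations. The release counts as met if the event grade equals the baseline grade or is at most 1.

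- Met at the trigger in 4 of 12: baseline 0 with event 0, baseline 0 with event 1, baseline 1 with event 1, baseline 2 with event 2. The first counts only if *any grade* is taken to include a value still in the normal range; without it the count is 3.
- Not met in the other 8, all with an event of Grade 2 or higher and above the baseline grade. There the rule has a working end point.

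These are logical cells, not probabilities.

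Do other sections close the gap? Take a patient with AST/ALT and bilirubin no higher than 1 × ULN at baseline. At the point of doubling:

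- AST/ALT ≤ 2 × 1 = 2 × ULN. This is inside the 3 × ULN entry limit and below the Hy's Law limit of more than 3 × ULN.
- Bilirubin ≤ 2 × 1 = 2 × ULN. This does not exceed the Hy's Law limit of more than 2 × ULN.

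More generally, any combined doubling with AST/ALT at or below 3 × ULN is outside Hy's Law, whatever the bilirubin. The cycle-start rule in 4.3 does not help either, because it accepts treatment-related toxicity of Grade 2 or less.

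**2. Grade 3 sentences.** Inputs: baseline grade 0, 1 or 2; peak at least 10 × ULN, yes or no; back to baseline grade within 7 days, yes or no. That gives 3 × 2 × 2 = 12 combinations.

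- Baseline Grade 0 or 1 (8 combinations): the rise is 3 or 2 grades, only the second sentence applies, and the dose goes down one level.
- Baseline Grade 2, peak below 10 × ULN (2 combinations): only the first sentence applies. Same dose if recovered within 7 days, otherwise one level lower.
- Baseline Grade 2, peak at least 10 × ULN, recovery after 7 days (1 combination): both sentences apply and both reduce by one level. No conflict.
- Baseline Grade 2, peak at least 10 × ULN, recovery within 7 days (1 combination): the first sentence gives the same dose, the second one level lower. **Conflict.**

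The size of the conflict follows from the levels in 4.3: 1000 versus 750 mg from the starting dose, 750 versus 500 mg from level -1. From level -2 it is 500 mg versus removal, since a third reduction is not allowed.

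**3. Against 4.3.2.** Section 4.3.1 describes a restart after Grade 4 enzymes and after the combined event. Section 4.3.2 discontinues for Grade 4 toxicity unless an exception applies (for laboratory values, ready correction within 72 hours without hospitalization) and for Hy's Law. Neither section refers to the other. The weekly recheck in 4.3.1 would not by itself show whether a 72-hour exception was met.

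**The case against.** Much can be said for a milder reading, and part of it stands.

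- *Grade 1 alone does not trigger the hold.* Correct. Both doublings are needed.
- *The hold is not empty.* A reader might infer that a patient can be re-dosed the same day with bilirubin still doubled. The documents do not support putting it so strongly: the rule includes a weekly recheck, *resolved* suggests a change from the triggering state, and the release names no analyte, so it may be meant to cover bilirubin. This makes the release undefined for such events; it does not show that immediate re-dosing is intended.
- *The combined rule does not produce different doses.* Correct. Every route under it ends one level lower. The argument about differing doses belongs only to the Grade 3 sentences.
- *The 10 × ULN limb must govern, because otherwise it has no work to do within Grade 3.* This is a fair textual argument and a site might adopt it. The table states no precedence, however, and the first sentence is written without a ceiling.
- *The combined rule sets an easier recovery standard than enzymes alone.* A reader might call this an error too. It is not shown to be one. Recovery to Grade 1 or baseline is also the general non-hematologic standard in 4.3.1, and the marked combined pattern meets discontinuation in 4.3.2. A different standard for a different trigger can be a deliberate choice.

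**Conclusion.** Two instructions in the AST/ALT rows do not work as written. The combined hold has no effective release condition when the doubled AST/ALT is Grade 1 or has stayed within its baseline grade, and its release does not say whether bilirubin must recover. The Grade 3 sentences give contradictory restart doses in one narrow case: at least 10 × ULN, less than a two-grade rise, and back to baseline grade within 7 days.

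The second point assumes a baseline of Grade 2 and a value of at least 10 × ULN that is still Grade 3. The entry limit of 5 × ULN shows that raised baseline values are allowed. It does not establish the grades, because the CTCAE v5.0 cut-offs are not reproduced in the documents. Nor is any event frequency given, so the number of patients affected cannot be estimated and is probably small.

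The two-stage design and its error rates are untouched. What is affected is liver-safety management, dose exposure and consistency between centers. Correction is worthwhile because a reduction cannot be undone and uses one of only two.

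**What to change.** Amend the AST/ALT rows of 4.3.1 so that:

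1. the combined rule has a release condition that the triggering result cannot already satisfy, and states which of AST, ALT and bilirubin must recover;
2. the two Grade 3 sentences are mutually exclusive, by saying which one governs a value of at least 10 × ULN that is less than two grades above baseline;
3. the restart wording after Grade 4 enzymes and after the combined event is reconciled with the discontinuation rules in 4.3.2, with the order of precedence stated.

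The thresholds, recovery levels and doses are for the sponsor's safety lead to choose; none is proposed here. The cost is a few words in one table and a cross-reference, by amendment. Sample size, endpoints and analysis do not change.

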**1.5 Summary of clinical trial findings**

In addition to these preclinical studies, the sEphB4-HSA has shown safety and tolerability in a first-in human phase I trial of 70 patients with advanced solid tumors. The study included a dose escalation phase and dose expansion phase at the maximum tolerated dose (MTD) or recommended phase II dose (RP2D). Dose levels tested were 2.5, 5, 10 and 15 mg/kg IV infusion weekly and 10, 15, and 20 mg/kg IV infusion every 2 weeks. No dose limiting toxicity was observed, except one patient with grade 3 hypertension not responsive to therapy in a patient at 20 mg/kg dose requiring dose reduction to 15 mg/kg and one patient with grade 3 QTc prolongation at 10mg/kg weekly. There were no grade 4 or 5 treatment related adverse events. The most common grade 3 toxicities were hypertension (27%), fatigue (16%), nausea (4%). Grade 1-2 toxicities included hypertension (48%), fatigue (35%), weight loss (13%), nausea (6%), and vomiting (5%). A maximum tolerated dose was not reached.

Pharmacokinetic studies showed a half-life of 306 hours. Based on these findings, the recommended phase II dose was established as 10mg/kg weekly and 20mg/kg every 2 weeks. Four of 70 patients had a partial or complete response and 50% showed stable disease [24]. The median number of cycles received was 2 (range 1-19). Several patients have received 4-11 months of therapy indicative of safety when used for prolonged period of time.

Clinical trials are planned to investigate its use as neoadjuvant therapy in genitourinary malignancies (NCT02767921) and metastatic bladder cancer in combination with checkpoint inhibitor ant-PD1 (NCT02717156).

**NU Study Number:** NU 18U10

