#### 4.2 Treatment Administration

Table 4-2-1: Premedications *			
Premedication	Dose	Route	Schedule
Diphenhydramine*	25 mg	Treating investigator discretion / Institutional standards	Administer at least 30 minutes prior to the sEphB4-HSA infusion
Acetaminophen*	650 mg	PO	Administer at least 30 minutes prior to the sEphB4-HSA infusion

\* Refer to Section 4.4.3 for (1) changes to the pre-medication regimen for patients who experience infusion reactions and (2) management of infusion reactions.

Table 4-2-2: Treatment Administration Summary					
Agent	Dose	Route	Schedule	Cycle Length	Supportive Therapies*
sEphB4-HSA	1000mg	IV over 60 minutes ( $\pm 15$ min)	Cycles 1-6: Day 1 of each cycle (14 days) Cycle 7+: Day 1 of each cycle (21 days)	Cycle 1-6: 14 days Cycle 7+: (21 days)	Antiemetics Additional medications for prophylaxis and supportive care can be administered as clinically indicated per Institutional standards.

\* Refer to Section 4.4.3 for the management of infusion reactions.

NU Study Number: NU 18U10

sEphB4-HSA will be administered intravenously. The dose of sEphB4-HSA will be 1000mg intravenously over 60 minutes ( $\pm 15$  min) on day 1 of a 14-day cycle. Beginning at Cycle 7, cycle length will be 21 days and patients will return for treatment on Day 1 of each cycle. Premedications include diphenhydramine and acetaminophen as described above in Table 4-2-1. Additional medications for prophylaxis and supportive care can be administered as clinically indicated per institutional protocol.

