## 5 STUDY PROCEDURES

Time Period	Screening (≤1 month unless otherwise indicated) 	On Treatment (1 Cycle = 14 Days)							Off Treatment	
		Cycle 1	Cycle 2	Cycle 3	Cycle 4	Cycle 5	Cycle 6	Cycle 7+ 	End of Treatment 	Follow -up 
Baseline	Week 1 Day 1	Week 3 Day 1	Week 5 Day 1	Week 7 Day 1	Week 9 Day 1	Week 11 Day 1	Week 13 Day 1			
Assessment or Activity										
Informed Consent	X									
Medical history 	X 								X 	
Physical exam 	X	X	X	X	X	X	X		X	
ECOG status	X	X	X	X	X	X	X		X	
Toxicity assessment		X	X	X	X	X	X		X	
Review Concomitant Medications	X	X		X		X			X	
Tumor Imaging 	X				X 				X	
CBC + diff, chemistry, liver enzymes *3, 4	X	X	X	X	X	X	X		X	
PSA *5	X	X		X		X			X	
EKG *6	X			X	As clinically indicated				As Clinically Indicated	
Research blood 	X					X			X	
Archival tissue sample 				X					X	
sEphB4-HSA administration 		X	X	X	X	X	X			
Survival Status										X

\*Can be completed  $\pm 3$  days of drug administration

- Includes vital signs (pulse, blood pressure) and height (baseline only) and weight.
- Bone scan, CXR or CT of chest, CT or MRI or abdomen and pelvis; with IV contrast if renal function adequate; the same modality used at baseline should be used throughout as clinically indicated. Imaging will occur at baseline and 2 months ( $\pm 7$  days) after starting therapy; thereafter, imaging will be conducted every 3 months ( $\pm 7$  days). After 1 year, imaging can be done every 4 months ( $\pm 7$  days) for patients with stable disease or better. Scans may also be conducted at any time, if clinically indicated.
- Study labs include: CBC with diff, alkaline phosphatase, albumin, total bilirubin, BUN, creatinine, calcium, glucose, AST, ALT, and electrolytes. These study safety labs are to be conducted within  $\leq 2$  weeks prior to registration.
- Testosterone level only at baseline.
- Assessment of response to therapy with PSA will occur on day 1 of odd cycles.
- Required for all patients at baseline and C3D1. Then only as clinically indicated thereafter.
- Blood will be collected at baseline, cycle 5 day 1, and at end of treatment for additional molecular analysis (see section 9).

**NU Study Number:** NU 18U10

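### For a first treatment-related Grade 3 hypertension still present on Day 1, Section 4.3.1 permits the infusion, Section 4.3 forbids it, and neither is given precedence

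*Combined protocol and SAP*

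**What the plan says.** Section 4.3 sets a condition for starting each cycle. Besides platelet and neutrophil thresholds, it requires "resolution of all treatment-related toxicity (except alopecia) to Grade 2 or less or to baseline when baseline was more than Grade 2". Alopecia and a baseline above Grade 2 are the only exceptions; hypertension is not exempted. When the condition is not met, "A dose can be delayed for up to 7 days for resolution of toxicity", and "If the dose cannot be given within 7 days of scheduled time it should be omitted".

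Section 4.3.1 has its own hypertension row. At Grade 3 it says "First occurrence, patients may continue on treatment while their antihypertensive therapy is optimized". It then adds: "A second occurrence of grade 3 hypertension despite antihypertensive therapy would require holding treatment with sEphB4-HSA until hypertension returns to" Grade 2 or less, after which dosing resumes one level lower.

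Table 4-2-2 schedules one infusion per cycle, on Day 1, every 14 days for Cycles 1 to 6 and every 21 days from Cycle 7. In the Section 5 calendars, the physical exam on each Day 1 carries the footnote "Includes vital signs (pulse, blood pressure) and height (baseline only) and weight".

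**The concern.** With one infusion per cycle, continuing on treatment without a hold means starting a new cycle. The hypertension row can therefore be taken to allow an infusion at Grade 3 blood pressure that the opening bullet of Section 4.3 rules out. Blood pressure is measured at the dosing visit, so the site has to settle the question there and then.

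A site following the hypertension row may infuse. A site following Section 4.3 delays for up to 7 days and then omits the dose. The choice can carry further: Section 4.3 removes patients who miss three doses in a row, and Section 4.5 ends treatment after a delay of 4 weeks or more. Section 11.6 requires adherence to the protocol as approved, so a site that doses through could be recorded as deviating although it followed a stated rule.

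The toxicity is a relevant one. Section 1.5 reports hypertension as the commonest Grade 3 toxicity in phase I (27%), and the dose-limiting events there include "one patient with grade 3 hypertension not responsive to therapy in a patient at 20 mg/kg dose requiring dose reduction to 15 mg/kg".

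**Working it through.** The plan states no figure on this point, so the main check is a comparison of the texts.

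**The rules side by side, for a first treatment-related event at Grade 3 on Day 1**

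| Rule | Infuse on Day 1? |
|---|---|
| 4.3, new-cycle condition | No, unless baseline was already above Grade 2 |
| 4.3.1, first Grade 3 occurrence | Permitted; no hold and no grade to return to |
| 4.3.1, second Grade 3 occurrence | No; hold to Grade 2 or less, then reduce one level |

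1. Both sections concern treatment-related toxicity, so both apply to this patient.
2. The row's contrast between first and second occurrence points to dosing through the first. If the Section 4.3 condition already barred dosing above Grade 2, the hold at the second occurrence would add nothing for the next dose except the dose reduction.
3. Sections 4.3, 4.3.1 (with the hypertension footnote and note), 4.3.2, 4.5, 5, 8.1.5 and 11.6 contain no statement of precedence and no exemption for hypertension.

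**How many patients could meet the conflict**

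Inputs: 15 patients in stage 1 and 25 in total (Section 10.1); 27% with Grade 3 hypertension and one therapy-unresponsive case among 70 patients (Section 1.5). Assumption: the phase I rate carries over.

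*Ceiling, any Grade 3 hypertension:* 15 × 0.27 = 4.05 and 25 × 0.27 = 6.75 patients. The chance of at least one in stage 1 is 1 − 0.73^15 = 0.991. If the rate were 15% to 40% (assumed range), the ceiling would be 3.75 to 10 of 25.

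*Patients at Grade 3 on a dosing day:* let s be the share of those patients who meet this condition. The documents do not give s. The per-patient rate is 0.27s, and the chance of at least one in n patients is 1 − (1 − 0.27s)^n.

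| s (assumed) | Rate | Expected of 25 | At least one of 25 | At least one of 15 |
|---|---|---|---|---|
| 5% | 0.0135 | 0.34 | 0.288 | 0.184 |
| 10% | 0.0270 | 0.68 | 0.496 | 0.337 |
| 25% | 0.0675 | 1.69 | 0.826 | 0.649 |
| 50% | 0.1350 | 3.38 | 0.973 | 0.886 |

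*Proxy from the unresponsive case:* 1/70 = 0.0143, giving 0.36 of 25 and 0.21 of 15 patients. The chance of at least one is 1 − (69/70)^25 = 0.302 in the full trial and 1 − (69/70)^15 = 0.194 in stage 1. The exact (Clopper-Pearson) 95% limits for 1/70 are 0.0004 and 0.0770, or 0.01 to 1.93 of 25 patients. A dose-limiting toxicity is a stricter event than being at Grade 3 on Day 1, so this proxy may be too low.

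**The case against.** The strongest reply is that a permission does not cancel a requirement. The hypertension row says patients may continue, Section 4.3 says what they must have, and a site that withholds complies with both. On this view the wording is at worst ambiguous, and being on treatment is a study status, as in the calendar's split between on- and off-treatment periods. Other rows of 4.3.1 also repeat holds that Section 4.3 already implies, so overlap at the second occurrence need not mean that the first is exempt. The general non-hematologic row orders interruption for unmanageable Grade 3 or 4 toxicity and does not list hypertension among its exclusions. There are safeguards too: uncontrolled hypertension is excluded at entry, Grade 2 already triggers antihypertensives and a recheck at one week, and patients are told to report poor control between visits.

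Part of this stands. Withholding does satisfy both rules, a combined reading is possible, the safeguards narrow the window, and the share s is assumed.

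The rest does not remove the conflict:

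- The same row speaks of holding and resuming treatment, where it plainly means dosing, so the status reading is weak.
- The rows that repeat a hold tighten or restate Section 4.3. The first-occurrence hypertension entry is the only one that expressly allows continuation at Grade 3.
- The general row depends on the toxicity being unmanageable, which does not describe a first event whose therapy is still being optimized.
- That withholding is safe under both rules does not tell a site that infusing under 4.3.1 breaches 4.3.

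**Conclusion.** The concern holds. For a first treatment-related hypertension that is Grade 3 on a dosing Day 1, one stated rule permits the infusion, another forbids it, and the protocol does not rank them. The textual finding needs no numerical assumption.

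Its practical size is small but uncertain. The ceiling is about 4.1 of 15 and 6.8 of 25 patients, if the phase I rate applies. The number actually exposed is 0.3 to 3.4 of 25 for an assumed s of 5% to 50%, and the imperfect proxy gives 0.36. What is at stake is infusion at Grade 3 blood pressure and different handling of the same patient at three centers. The tabulation of adverse events by maximum grade in Section 10.2 would change little, and the two-stage design is untouched. It should be corrected because it concerns a dosing rule for the commonest Grade 3 toxicity seen in phase I.

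**What to change.** Preferred: amend the Grade 3 hypertension row so that at a first occurrence the patient stays on study at the same dose level while antihypertensives are optimized, and the next infusion is given only once hypertension is Grade 2 or less (or at baseline), as Section 4.3 requires. The existing delay and omission rules then apply.

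Alternative, if the sponsor intends dosing through: add to the Section 4.3 bullet an exemption for first-occurrence Grade 3 hypertension managed under 4.3.1.

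Either option costs one sentence in an amendment and a memo to the sites, with no added visits or patients. Under the preferred option, a few doses will be delayed by up to 7 days or omitted.

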Neutropenia	Neutropenic fever or Grade 4 neutropenia	Hold therapy, recheck weekly, initiate retreatment when resolved to Grade 1 or less and restart treatment with a one level dose reduction.
Anemia	Grade 1 or Grade 2 (Hemoglobin (Hb) $> 8$ g/dl)	Investigate and manage as deemed appropriate by the investigator with or without interruption of study drug or change in dose, taking into account previous history of anemia. Common treatable causes of anemia (e.g., iron, vitamin B12 or folate deficiencies and hypothyroidism) should be excluded. In some cases management of anemia

NU Study Number: NU 18U10

		may require blood transfusions.
	Grade 3 (Hb < 8g/dl) or worse	
Study treatment should be interrupted for up to maximum of 4 weeks to allow for bone marrow recovery and the patient should be managed appropriately. Study treatment can be restarted at the reduced dose level -1 if Hb has recovered to > 10 g/dl. Any subsequently required anemia related interruptions, considered likely to be dose related, or coexistent with newly developed neutropenia, and or thrombocytopenia, will require a further study treatment dose reduction to level -2.
 
If a patient has been treated for anemia with multiple blood transfusions without study treatment interruptions and becomes blood transfusion dependent as judged by investigator, study treatment should be permanently discontinued.

1. All patients will be educated about the hypertension side effect and instructed to contact the study team if their blood pressure remains under poor control between visits. The patients may be asked to keep a blood pressure log as per treating physician discretion.

*NOTE: Stopping or reducing the dose of study drug can cause a decrease in BP. The treating physician should monitor the patient for hypotension and adjust the number and dose of antihypertensive medication(s) accordingly.*

If the patient experiences a grade 4 allergic or hypersensitivity reaction the drug should be permanently discontinued.

AR targeted therapy will continue per standard of care regardless of sEphB4-HSA toxicity.

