#### 4.3.2 Toxicities that require discontinuation from protocol therapy

Protocol therapy should be discontinued if a patient experiences:

- Any CTC Grade 4 toxicity with the exception of:
  - CTC Grade 4 neutropenia of 5 days or fewer duration
  - CTC Grade 4 nausea/vomiting or diarrhea that resolves to Grade 3 or less within 72 hours despite optimal supportive care.
  - CTC Grade 4 laboratory abnormalities that can be readily corrected within 72 hours and do not result in hospitalization.
- CTC Grade 3 thrombocytopenia with hemorrhage
- CTC Grade 3 febrile neutropenia
- Hy's Law (AST or ALT >3x ULN with concomitant serum bilirubin >2x ULN and no alternate etiology)

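### Sections 4.3.1 and 4.3.2 give conflicting instructions for some toxicities, most clearly febrile neutropenia, and nothing says which section governs

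*Combined protocol and SAP*

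**What the plan says.** Section 4.3.1 is a table of dose modifications for treatment-related toxicity. Its neutropenia row is triggered by "Neutropenic fever or Grade 4 neutropenia", with no limit on the grade of the fever or the duration of the neutropenia, and its action is "Hold therapy, recheck weekly, initiate retreatment when resolved to Grade 1 or less and restart treatment with a one level dose reduction". The Grade 3/4 platelet row uses the same action. The general non-hematologic Grade 3/4 row withholds drug until recovery and then lowers the dose one level. Rows for nausea, vomiting and diarrhea, for AST/ALT, and for anemia also provide for a restart at a lower dose.

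Section 4.3.2 lists toxicities for which protocol therapy should be discontinued:

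- Every Grade 4 toxicity, apart from three cases. The first is "CTC Grade 4 neutropenia of 5 days or fewer duration". The second is nausea, vomiting or diarrhea that has come down to Grade 3 or better by 72 hours. The third is a laboratory abnormality that is readily put right in the same time and does not lead to a hospital stay.
- For low platelets with bleeding, the entry reads "CTC Grade 3 thrombocytopenia with hemorrhage".
- For neutropenia with fever, the entry reads "CTC Grade 3 febrile neutropenia".
- The last entry is Hy's Law, defined there as AST or ALT above 3x ULN with bilirubin above 2x ULN and no other cause.

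Neither subsection mentions the other. The general rules that open 4.3 do not rank them, 4.5 refers to section 4.3 as a whole, and 4.7 lists reasons for removal without addressing the question.

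**The concern.** A site that reads only the relevant row of 4.3.1 would hold drug, wait for recovery and re-dose one level lower. A site that reads 4.3.2 would stop the same patient permanently. With three centers, the same event could be handled both ways. The more serious outcome is renewed exposure of a patient whom the protocol elsewhere says must come off treatment. The withdrawal rule in 4.3 for failure to recover within 4 weeks does not help, because the patients 4.3.1 restarts are those who do recover.

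**Working it through.** The check is a comparison of text, with a short calculation for size. Each restart in 4.3.1 was set against each stop rule and exception in 4.3.2.

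| Event | 4.3.1 | 4.3.2 | Result |
|---|---|---|---|
| Grade 3 febrile neutropenia | Restart one level lower | Stop, no exception | Direct conflict |
| Grade 4 general non-hematologic toxicity | Restart one level lower | Stop unless an exception applies | Direct conflict |
| Grade 3 platelets with hemorrhage | Restart; bleeding not mentioned | Stop | Overlap, no cross-reference |
| Grade 4 neutropenia beyond 5 days | Restart | Stop | Overlap, no cross-reference |
| Grade 4 nausea, vomiting or diarrhea not down to Grade 3 in 72 hours | Resume one level lower | Stop | Overlap, no cross-reference |
| Grade 4 AST/ALT, platelets or anemia, not readily corrected in 72 hours or leading to hospitalization | Restart lower | Stop | Overlap, no cross-reference |
| AST/ALT events meeting Hy's Law | Restart lower | Stop | Overlap, no cross-reference |
| Grade 4 neutropenia of 5 days or fewer, no fever | Restart | Excepted | No conflict |
| Grade 4 hypertension | Withhold; no restart stated | Stop | No conflict |
| Grade 4 allergic reaction | Permanently stop | Stop | No conflict |

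**Why the first two rows are direct conflicts.** In the neutropenia row, fever is itself a named trigger for restart. If 4.3.2 prevails, Grade 3 drops out. What remains is fever graded below 3 and Grade 4 events that fit an exception. In the general non-hematologic row, nausea, vomiting and diarrhea are excluded and neutropenia does not belong, so the laboratory exception is the only one of the three that could apply. A Grade 4 clinical event in that row always meets the stop rule.

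**Hy's Law.** The 4.3.1 row on concurrent AST/ALT and bilirubin doubling is read here as covering rises of at least twofold. Take ALT from 0.8x to 3.2x ULN and bilirubin from 0.6x to 2.4x ULN. Each ratio is 4 (3.2/0.8 and 2.4/0.6), so both have at least doubled, and 3.2 > 3 and 2.4 > 2. Absent another cause, this patient meets both rules from normal baselines. Raised baselines are therefore not needed. The Grade 3 and Grade 4 AST/ALT rows carry no Hy's Law exception, so they can overlap too.

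**Size.** Section 1.5 reports no treatment-related Grade 4 or 5 event in 70 phase I patients.

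- One-sided 95% upper bound: 1 − 0.05^(1/70) = 0.0419, or 4.2%.
- Expected number among 25 patients at that rate: 25 × 0.0419 = 1.05.
- Probability of 2 or more among 25 at that rate: 1 − 0.9581^25 − 25 × 0.0419 × 0.9581^24 = 1 − 0.343 − 0.375 = 0.28.

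So 1.05 is an expected count at the bound, not a maximum. The bound covers all related Grade 4 and 5 events, including those with no conflict. It pools doses from 2.5 to 20 mg/kg on two schedules with a median of 2 cycles. For Grade 3 febrile neutropenia, Grade 3 thrombocytopenia with hemorrhage and Hy's Law, the documents give no rate.

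**The case against.** The best defense is that 4.3.1 gives the default and 4.3.2 the specific stop. The heading of 4.3.2 speaks of required discontinuation, its events are mostly narrower than the rows of 4.3.1, and its exceptions leave many Grade 4 restarts something to apply to. The protocol needs this kind of reading elsewhere: 4.3.3 permanently stops drug after a Grade 3 infusion reaction, although the general non-hematologic row would restart. There are also safeguards. Sections 4.5 and 4.7 let the physician stop treatment, SAEs are reported within 24 hours (7.3.3.1), and the trial is under High Risk monitoring.

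Much of this stands. For platelets with bleeding, prolonged Grade 4 neutropenia, the 72-hour cases and Hy's Law, a careful reader can reconcile the two sections, and the fault is a missing cross-reference. A reader might infer that nearly every row of 4.3.1 contradicts 4.3.2; the documents do not support that.

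The defense does not settle febrile neutropenia or Grade 4 general non-hematologic toxicity, where the 4.3.1 text restarts the very event that 4.3.2 stops. The precedence it relies on is also inferred. Section 4.3.1 contains its own permanent stops (Grade 4 allergic reaction, transfusion-dependent anemia), so a reader could take silence in the other rows as permission to restart. The safeguards report and review events, or allow a physician to stop; none says which rule applies.

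**Conclusion.** The inconsistency is real and should be corrected. It is direct for Grade 3 febrile neutropenia and for Grade 4 general non-hematologic toxicity outside an exception; elsewhere it is an overlap without a stated order of precedence. The events are expected to be uncommon, on the strength of 0 of 70 related Grade 4 or 5 events in phase I. That evidence does not cap the rate under continued 1000 mg dosing, and nothing in the documents sizes the Grade 3 and Hy's Law events.

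A reader might also infer that the trial's error rates or its primary result are at risk. They are not: the conflict concerns dosing after toxicity and changes no Simon figure and no endpoint definition. It is a matter of patient safety and consistent conduct. The conclusion rests on the current text alone and assumes that no precedence rule exists in a document not provided.

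**What to change.** Make three changes to 4.3.1:

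1. State at its head that 4.3.2 governs whenever an event meets one of its criteria.
2. Remove Grade 3 febrile neutropenia from the restart row for neutropenia. If re-treatment is in fact intended, delete it from 4.3.2 instead.
3. Limit the Grade 4 restart in the general non-hematologic row to events that meet a 4.3.2 exception.

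Restricting the platelet row to events without hemorrhage, and excluding Hy's Law cases from the AST/ALT rows, would help the reader but follows from the first change.

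The cost is a text amendment. It adds no procedure or visit and leaves the sample size and endpoints as they are.
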